2.2.2 Secondary endpoints/outcomes

Secondary endpoints/outcomes included:

- Cumulative incidence of the composite primary endpoint at week 48
- Proportion of patients with HIV-RNA viral load <50 copies/mL at week 24, 36, 48
- HIV-1 drug resistance at confirmed virological failure [Time Frame: Through study completion, an average of 1 year]
- Time to reach CD4 count >200/ μ L (first measurement)
- Proportion of patients with CD4 cell count < 200 μ L and < 350 μ L at week 4, 8, 12, 24, 36, 48
- CD4/CD8 ratio at week 4, 8, 12, 24, 36, 48
- Incidence of IRIS in the two arms through week 48
- Incidence and duration of hospitalisation or rate of relapse of specific opportunistic infection (OI) or bacterial infection (BI) through week 48
- Number and proportion of participants with Grade 2, 3 and 4 adverse events (AEs), treatment-related AEs, AEs leading to the study drug discontinuation, and death through week 48
- ART and OI/BI treatment changes and dose modifications due to toxicities and DDI with ART, and IRIS through week 48
- Healthcare resource use, including total inpatient days and emergency room visits through week 48
- QOL and functional status outcomes, including overall self-reported QOL and functional status compared in the two groups at week 48
- Discontinuation or modification of study medication due to insufficient virological response, resistance mutations at baseline, or resistance mutation development before week 48

2.2.3 Exploratory endpoints/outcomes

- Mutations detected by deep sequencing compared with those detected by population sequencing
- Proportion of patients with HIV-RNA viral load < 50 copies/mL at week 4, 8, 12

3. STUDY METHODS

3.1 GENERAL STUDY DESIGN AND PLAN

LAPTOP study is an international, open-label, randomised, two arm, multicentre trial over 48 weeks to compare two strategies for HIV-1 infected patients with advanced disease.

Eligible patients will be randomised to receive either an integrated inhibitor containing regimen (B (50mg)/F (200mg)/TAF (25mg) [1 pill administered orally once daily for 48 weeks]) or a boosted PI regimen (D (800mg)/C (150mg)/F(200mg)/TAF (10mg) [1 pill administered orally once daily for 48 weeks]). Randomisation is stratified by country and baseline CD4 cell count (<50 cells/ μ L, 50-199 cells/ μ L, or \geq 200 cells/ μ L).

[figure not shown]

Figure 1: Study design

Study participants will be ART-naïve, HIV-1-infected individuals aged 18 or older who have at entry HIV viral load > 1000 copies/ml and at least one of the following: i) have AIDS with any CD4 cell count; ii) have severe bacterial infection (BI) and must have a CD4 cell count < 200/µl within 30 days prior to study entry; iii) are asymptomatic with CD4 cell count < 100/µL within 30 days prior to study entry; iv) are currently receiving treatment for OI. Women who were pregnant or breastfeeding or who declined a contraceptive method at screening were not eligible.

After the screening visit, participants will be seen at baseline, when they initiated c-ART and weeks 4, 8, 12, 24, 36 and 48, as well as a follow-up visit 30 days following the week 48 visit.

At each visit, participants will have routine safety monitoring as well as measurement of plasma HIV-1 RNA viral load, CD4, CD8 cells counts and a deep sequence resistance test. In the event of virological failure, local resistance tests should be performed on the first sample, and participants should discontinue study treatment and receive rescue therapy at the investigators' discretion.

Quality of life (QoL) questionnaire (EuroQoL EQ-5D-3L) and HIV Symptom Index (HIV-SI/SDM) questionnaire will be administrated at each visit from baseline.

3.2 RANDOMISATION SCHEME AND BLINDING

The randomization list will be generated by an independent statistician not part of the study team. The list will be generated by a centralized computer-generated random list with a permuted block size. He is the only person who know the size of the blocks.

Participants will be randomly assigned, in a 1:1 ratio, to receive a BIC containing regimen or boosted PI containing regimen for 48 weeks, with allocation stratified by country and baseline CD4 cell count (<50 cells/µL, 50-199 cells/µL, or ≥200 cells/µL).

Randomization will be done at the baseline visit (date of the study treatment initiation). This study is open-label; therefore, all investigators, site pharmacists, study nurses and participants will be unmasked and aware of the treatment allocation throughout the study.

3.3 STUDY SCHEDULE

Procedure	Screening Visit	Baseline Visit ²	Treatment Phase						Follow Up/Early Termination Visit
	Day -28 to Enrolment ¹		Week 4 (± 7 days)	Week 8 (± 7 days)	Week 12 (± 7 days)	Week 24 (± 7 days)	Week 36 (± 7 days)	Week 48 (± 7 days)	30 days following Week 48 visit (± 7 days)
Informed consent	X								
Eligibility assessment ³	X								
Demographics	X								
Medical and social history ⁴	X								
ECG ⁵	X								
HBV and HCV testing ⁶	X								
TB test ⁷	X								
Local Resistance testing ⁸	X								X
Randomisation		X							
Symptom-directed physical examination		X	X	X	X	X	X	X	X
Vital signs ⁹	X	X	X	X	X	X	X	X	X
Urinalysis ¹⁰		X			X	X	X	X	X
Haematology (including CD4 & CD8 testing) ¹¹	X	X	X	X	X	X	X	X	X
Clinical chemistry ¹² (including urinary chemistry)	X	X	X	X	X	X	X	X	X
Viral load testing ¹³	X	X	X	X	X	X	X	X	X
Sample collection for central resistance testing (deep sequencing) ¹⁴		X	X	X	X	X	X	X	X
Concomitant medications	X	X	X	X	X	X	X	X	X
Adverse event assessments		X	X	X	X	X	X	X	X
Quality of Life questionnaire (EuroQoL EQ-5D-3L)		X	X	X	X	X	X	X	X
HIV Symptom Index questionnaire (HIV-SI/SDM)		X	X	X	X	X	X	X	X
Dispensing of trial drugs ¹⁵		X			X	X	X		
Adherence ¹⁶					X	X	X	X	
Serum pregnancy test ¹⁷	X								
Urine pregnancy test ¹⁸		X	X	X	X	X	X	X	X
Physical examination (including height & weight) ¹⁹	X	X	X	X	X	X	X	X	

Assessment sub notes		Parameters/Notes
1	Screening visit	
The maximum time between screening visit and baseline visit is 28 days; however, participants should be invited for their baseline visit as soon as reasonably possible in order to start their treatment.
 
Only the following laboratory assessments are required for screening and historic (up to 28 days old) tests results may be used for screening:
 
 • HBV and HCV testing • TB test • CD4 & CD8 testing • Platelet count testing • Clinical chemistry (only creatinine, creatinine clearance, eGFR, potassium, sodium, ALT, AST is required) • Viral load testing • Resistance testing (the last resistance test carried out can be used) 
A serum pregnancy test is mandatory at the screening visit for women of child bearing potential

2	Baseline visit	
For baseline results, all screening tests carried out within 10 days before baseline can be used. This includes historic screening results, as long as they fall within the 10 day window before baseline. Screening data obtained more than 10 days from baseline, must be repeated at baseline.

3	Eligibility	According to the inclusion/exclusion criteria.
4	Medical & social history	
Including:
 
 • Recreational drug use • Smoking history • Alcohol intake • Concomitant diseases • Past & present medical history, including HIV- associated conditions • Review of any medication taken within the last 30 days
5	ECG	12-Lead ECG performed supine. If an ECG is not performed at screening, it must be performed by the time of the baseline visit.
6	HBV & HCV testing	
HBV antigen test and hepatitis C (HCV) antibodies test (if patient tests positive for HCV antibodies, test for HCV RNA, if positive and chronic for either HBV or HCV, add HBV DNA test at baseline visit).
 
HBV test to be repeated in event of positive result. Participants with active HBV infection at study entry will be monitored throughout the study and additional HBV DNA tests performed at the Week 24 and 48 visits. For screening, test results 28 days prior to the screening visit can be used

7	TB Testing	
A TB test (IGRAs e.g. ELISOT, QuantiFERON) will be performed in patients with expected latent TB at the screening visit. For screening, test results 28 days prior to the screening visit can be used. Patients can be randomised into the study without having the latent TB screening results available at randomisation
 
A TB test can be performed at subsequent visits on the basis of clinical suspicion.

8	Resistance testing (performed locally)	
A local resistance test will be performed at the screening visit. This result is not required for eligibility or prior to randomisation. If a HIV resistance test was done previously and results are available, the last resistance test carried out shall be considered.
 
An additional resistance test will be performed at the ETV for patients with virological failure or insufficient virological response.

9	Vital Signs (10 mins resting)	
Including:
 
 • Pulse • Blood pressure
10	Urinalysis	
Including:
 
 • Urinary creatinine* • Urinary glucose (dipstick test sufficient)* • Urinary proteins* • Albumin (can be obtained from 'spot' urine test) • Nitrites (dipstick test sufficient) * • Albumin: Creatinine Ratio (ACR) and Protein: Creatinine Ratio (PCR) • Urinary phosphate • Beta-2 microglobulin • Leukocytes (dipstick test sufficient)

		* Assessments should be performed as per local site procedure; however, assessments marked with an asterisk are mandatory for the study at and after baseline.
		Including: 
● Platelet count*● RBC Count (indices MCV & MCH)*● WBC count (absolute)*● CD4 Count and %*● CD8 Count and %*● Haemoglobin*● Haematocrit*
11	Haematology (non-fasting)	RBC Count indices: 
● MCV● MCH Automated WBC differentials: 
● Neutrophils*● Lymphocytes*● Monocytes● Eosinophils● Basophils
		* Assessments should be performed as per local site procedure; however, assessments marked with an asterisk are mandatory for
		the study.
		Assessments that have been underlined are required at screening (results up to 28 days old can be used).
		
● Urea*● Chloride*● Alkaline phosphatase*● Creatine phosphokinase*● Creatinine*● Calcium*● Phosphate*● Creatinine clearance, eGFR*
12	Clinical chemistry (non-fasting)	(Calculations: Cockcroft-Gault (requires weight), MDRD, CX-Epi) 
● Glucose*● Total* and indirect bilirubin● Potassium*● Total protein*● Sodium*● ALT*● AST*● Albumin*● Cholesterol*● HDL*● LDL*● Triglycerides*
		* Assessments should be performed as per local site procedure; however, assessments marked with an asterisk are mandatory for the study at
		and after baseline.
		Assessments that have been underlined are required at screening (results up to 28 days old can be used).
13	Viral load testing	HIV RNA viral load-results obtained 28 days prior to screening can be used.

14	Resistance testing for deep sequencing (sent to central laboratory)	In addition to the resistance test performed locally, a resistance testing sample will be taken at the Baseline visit, each visit in the treatment phase (Week 4, 8, 12, 24, 36 and 48) and at the ETV (for patients with virological failure identified outside of a scheduled visit). All resistance testing samples for patients with virological failure will be sent to a central laboratory for next generation sequencing to look for low-level pre-existing resistance in cases of suspected resistance development.
15	Drug dispensing	There will be four dispensations of the study medication to the patient (Baseline visit, Week 12, 24 and 36).
16	Adherence	Also performed at the ETV if required.
17	Serum pregnancy test	For women of child bearing potential only (see Appendix 7 for definition).
18	Urine pregnancy test	Dipstick and urine pregnancy test (WOCBP only - see Appendix 7 for definition). This is a mandatory assessment. If a urine pregnancy test is not possible, a serum pregnancy test can replace this.
19	Physical examination	Weight is required at all visits, as detailed in the appendix 1, however height is only required at baseline.

4. SAMPLE SIZE CALCULATION

In the ANRS 146 OPTIMAL trial [Levy et al.], of late presenters, the proportion of patients with severe morbidity (new adverse drug event (ADE), other HIV related diseases, serious non-AIDS events, IRIS and death) was estimated at 12.2% per year in the boosted PI arm. The virological failure was estimated at 20% at week 48 in the DRV/r group of the IMEA 040 DATA study (Slama L et al) that recruited a similar population. As a few subjects will meet more than one of these criteria, we assumed a cumulative probability of failure at 25% at 48 weeks in the PI regimen group.

A total of 404 evaluable subjects, randomized in a 1:1 ratio to 2 treatment groups (202 subjects per treatment group), achieves at least 80% power to detect a non-inferiority margin of 1.606 in the hazard ratio, which corresponds to a 12% difference in the cumulative probability of failure rate between INI-based regimen group (37%) and PI-based regimen group (25%), with 97 events required. The sample size and power calculation assume that the cumulative probability of failure is 25% for the PI regimen group and 23% for the INI-based regimen group (i.e. the expected hazard ratio is 0.909), using a non-inferiority margin of 1.606 in hazard ratio and a two-sided 95% confidence interval (CI). The sample size and power calculation were made using the statistical software package nQuery Advanced, non-inferiority testing of two survival curves using cox regression module (Version 8.1.2.0).

With an estimated ~7.5% drop off rate/year, we plan to enrol 220 subjects per group to ensure we have sufficient power for this per-protocol analysis.

Superiority of INI-based regimen group versus PI-based regimen group will be evaluated after the non-inferiority is established. With an ITT analysis, 440 subjects and 78 events, a two-sided log-rank test at an alpha level of 0.05 will achieve at least 80% power to detect a 50% reduction in hazard rate in INI-based regimen (i.e. the hazard ratio is 0.5). A 50% reduction in hazard rate means that INI-based regimen could decrease the risk by 11.6% (25% for PI- vs 13.4% for INI- based regimen).

5. GENERAL CONSIDERATIONS

All continuous variables will be summarised using the following descriptive statistics: n (non-missing sample size), mean, standard deviation (SD), 1st quartile, median, 3rd quartile, maximum and minimum. The frequency and percentages (based on the non-missing sample size) of observed levels will be reported for all categorical variables.

The number of participants and the flowchart of the study will be presented. The period of enrolment and the total number of participants screened to be included in the study will be presented. The number of ineligible participants and the total number of randomized participants will be presented.

The number of participants who never receive the study intervention will also be presented by treatment group and those who were included in the full analysis set and the safety analysis set will be presented.

Baseline is considered as the day 1 visit and the baseline data is data collected just before intervention at day 1.

5.1 TIMING OF ANALYSES

Before the final analysis is performed, the trial Statistician will write the statistical code needed to perform the statistical analyses required by the SAP. A temporary version of the trial database should be sent to the Trial Statistician for final SAP and code preparation. The code together with the temporary version of the trial database will result in a mock-up report. The Trial Statistician will review the mock-up report, and subsequently the SAP will be updated if needed before the final version is approved and signed-off. The final analysis will be performed after the database has been locked and cleaned and this analysis plan has been validated and signed.

5.2 ANALYSIS POPULATIONS

For the purposes of analysis, the following analysis sets are defined.

5.2.1 Full Analysis Population

Modified Intention-to-treat (mITT) analysis set: all randomised participants who received at least one dose of study drug. Participants will be included in the analyses according to the planned randomised intervention.

The following data points sets are defined:

- **DPS1:** All observed data will be included in the analysis set regardless of study intervention discontinuation and/or receipt of rescue therapy
- **DPS2:** For participants who discontinue study intervention and/or receive rescue therapy, post-discontinuation or post-rescue observations will be excluded.

The mITT and DPS1 will be used to estimate the primary endpoints and the all secondary endpoints.

5.2.2 Per Protocol Population

The per-protocol (PP) population will include all participants from the mITT population, with the exception of those who did not meet the inclusion/exclusion criteria or who initially received treatment assigned to the other group.

The PP and DPS2 will be used for sensitivity analyses of the primary endpoint.

5.2.3 Safety Population

Safety analysis set: all participants who are exposed to a study intervention. Participants will be analysed according to the planned randomised intervention.

The safety analysis set is used to analyse the endpoints and assessments related to safety.

Safety analysis set and DPS1 will be used to present safety data.

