6.2 PROTOCOL DEVIATIONS

The following deviations are defined for the purpose of analysis:

- Did not fulfil the eligibility criteria
- Interruption of study treatment for >10% of total time on treatment
- Received treatment from another randomisation group
- Consent withdrawal
- Lost to follow-up (at least 2 consecutive visits missed until the end of the study)
- At least one missed follow-up visits for those not lost to follow-up

At least one visit for which the viral load is missing for those for whom all visits have been madeA summary table by treatment group and overall with the number and percentage of subjects presenting deviations will be prepared for the subjects in the mITT population.

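### The SAP's safety set repeats the mITT set by randomised arm, so no table shows adverse events by the regimen being taken; an as-received table should be added beside the by-arm one.

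*Combined protocol and SAP*

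**What the plan says.** SAP 5.2.3 gives the membership: "Safety analysis set: all participants who are exposed to a study intervention". It then fixes the grouping: "Participants will be analysed according to the planned randomised intervention". It also fixes the data: "Safety analysis set and DPS1 will be used to present safety data". SAP 5.2.1 defines DPS1: "All observed data will be included in the analysis set regardless of study intervention discontinuation and/or receipt of rescue therapy".

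The mITT set in SAP 5.2.1 is "all randomised participants who received at least one dose of study drug", with the matching grouping rule: "Participants will be included in the analyses according to the planned randomised intervention".

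SAP section 8 counts person-time from baseline to the week 48 visit, or to death, study discontinuation or loss to follow-up if earlier, whichever drug is being taken. It compares incidence rates between groups named BIC and DRV/c. The endpoints include drug-related events, drug-related grade 3-4 events and events leading to discontinuation.

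The documents provide for treatment with the other arm's regimen in three places:
- Protocol 6.1.3 lets a DRV-arm participant move to the BIC arm if specified DRV-resistance patterns come to light after randomisation.
- SAP 6.2 has a deviation category, "Received treatment from another randomisation group".
- SAP 5.2.2 removes from the per-protocol set anyone "who initially received treatment assigned to the other group". That set is for sensitivity analysis of the primary endpoint, not for safety.

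**The concern.** A separately named safety set usually exists so that harms can be read against the drug taken. Here it has the same members, the same grouping and the same data rule as mITT, so it adds nothing to the efficacy set.

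The safety endpoints are also partly about drugs. Under protocol 8.2.2 the investigator judges causality against study drug. If a participant randomised to DRV/c has moved to BIC and then has an event judged related to BIC, SAP section 8 counts it as a drug-related event in the DRV/c column. A reader of SAP Table 7 could not see this. At stake is the reading of uncommon drug-related events, where a few cases in the wrong column can change the impression.

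**Working it through.** The plan states no figure to reproduce on this point. The check compares definitions and then illustrates size.

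**Step 1: are the two sets the same?**

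| | mITT (SAP 5.2.1) | Safety (SAP 5.2.3) |
|---|---|---|
| Members | Randomised, at least one dose | Exposed to a study intervention |
| Grouping | Planned randomised arm | Planned randomised arm |
| Data | DPS1 | DPS1 |

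They could differ only by someone exposed but never randomised, and such a person has no planned arm to be analysed under. The sets are therefore the same.

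**Step 2: which events end up under a regimen not being taken?**
- Participant started on the wrong regimen: events for as long as that regimen is taken.
- Participant who switches from DRV/c to BIC later: only events that start after the switch. Earlier events are correctly placed.

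DPS1 and the follow-up rule in section 8 keep the post-switch events and person-time in the randomised column. The SAP specifies no analysis by regimen received.

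**Step 3: how large could the effect be?** The documents give no crossover count, so the shares below are assumptions. Let r be the true rate ratio (BIC/DRV) and f the share of an arm's person-time spent on the other regimen. Assume that event rates depend only on the drug being taken at the time.

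If only DRV-arm participants cross, the DRV-arm rate is a mixture and the by-arm ratio is

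r / [(1 - f) + f·r].

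If both arms cross by the same share, it is

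[(1 - f)·r + f] / [(1 - f) + f·r].

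Example, one-way, r = 0.50, f = 0.02: 0.50 / (0.98 + 0.01) = 0.505.

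| f | r = 0.50, one-way | r = 0.50, two-way | r = 2.0, one-way | r = 2.0, two-way |
|---|---|---|---|---|
| 1% | 0.503 | 0.508 | 1.98 | 1.97 |
| 2% | 0.505 | 0.515 | 1.96 | 1.94 |
| 5% | 0.513 | 0.538 | 1.90 | 1.86 |
| 10% | 0.526 | 0.579 | 1.82 | 1.73 |

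Every entry moves toward 1. In head counts, 1% to 3% of the planned 440 (220 per arm) would be 4.4 to 13.2, so about 4 to 13 people; that percentage is also an assumption. Sample size, power and the type I error rate are unaffected.

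**The case against.** The strongest reply is that by-arm safety is what the protocol prescribes. The trial is described as a comparison of two strategies. Protocol 9.3 keeps participants who switch in their randomised group, and protocol 9.3.3 places all secondary outcomes, safety among them, on the ITT population. SAP 5.2.3 carries that rule over. This stands: a reader might infer that the SAP has made an error or departed from the protocol, and the documents do not support that.

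Three further replies also stand:
- The deviation category and the per-protocol exclusion provide for other-arm treatment in case it happens; they do not predict how often. The one arm-to-arm switch that the protocol spells out runs from DRV to BIC only, and needs specific resistance patterns found after randomisation.
- Regrouping everyone by first regimen taken would correct initial misdosing only. Someone who switched from DRV/c to BIC later would stay under DRV/c.
- Replacing the by-arm table would give up the randomised comparison and put discontinuations and deaths in SAP Table 7 on a different basis from the same events in SAP Table 2.

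It can also be said that the information is available elsewhere. This stands only in part. SAP 6.2 tabulates deviations by group, and SAP 10.1.1 lists treatment changes with dates and reasons. But the SAP 10.1.1 list covers changes for toxicity, drug interaction or IRIS, which is not the reason for a resistance-driven switch under protocol 6.1.3. Neither output reassigns an event or its person-time.

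**Conclusion.** The point holds as a minor gap. The safety set duplicates mITT, and the plan has no view of adverse events by regimen being taken, although its safety tables are labelled by drug and include drug-related events. The by-arm analysis itself is defensible and should stay.

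Two stronger readings are tempting. One is that every event in a crossover participant is charged to the wrong drug; that is true only of someone who never took the assigned regimen. The other is that safety differences in general are materially diluted. With up to 10% of DRV-arm person-time on BIC, a true ratio of 0.50 is still reported as 0.526, and the shares that produce even that shift are assumed, not documented. Actual crossover may be close to zero.

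What remains is a bias toward 1, probably small for overall rates, that matters mainly for rare drug-related grade 3-4 events. The direction rests on event rates following the drug currently taken; the size rests on a crossover share that the documents do not give.

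**What to change.** Keep the safety table by randomised arm and name it as the strategy comparison that protocol 9.3 and 9.3.3 call for. Add to SAP 5.2.3 and section 8:

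- A safety analysis by regimen actually received, with each event assigned to the study regimen being taken at onset and person-time divided in the same way.
- Time and events on neither study regimen shown separately. This includes time off treatment, and the alternative regimens mentioned in protocol 6.1.3 and in the note to the primary endpoint.
- A listing of events that start after a switch, showing the randomised arm, the regimen at onset and the date of change.

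This gives the safety set a function and uses data already collected. SAP 5.1 allows the plan to be updated before sign-off. Because the analysis is added and replaces nothing, the protocol's rule for switchers is left intact.

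The cost is one extra table and one listing. For the few who switch, the as-received comparison is not protected by randomisation, so it should be read beside the by-arm table and not in place of it.
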